27. APPENDIX E: QUALITY OF LIFE (SF-12)

Your Health and Well-Being

This survey asks for your views about your health. This information will help keep track of how you feel and how well you are able to do your usual activities. Thank you for completing this survey!

For each of the following questions, please mark an \boxtimes in the one box that best describes your answer.

1. In general, would you say your health is:

2. The following questions are about activities you might do during a typical day. Does your health now limit you in these activities? If so, how much?

	Yes, limited a lot	Yes, limited a little	No, not limited at all
	lacktriangle	lacktriangle	lacktriangle
Moderate activities, such as moving a table, pushing a vacuum cleaner, bowling, or playing golf	🔲 1	2	3
ь Climbing several flights of stairs	🔲 1	2	3

CUC10-LNG06-04 Page 36 of 38

4.

3. During the past 4 weeks, how much of the time have you had any of the following problems with your work or other regular daily activities as a result of your physical health?

	All of	Most	Some	A little	None
	the	of the	of the	of the	of the
	time	time		time	time
				· ·	
	\blacksquare	lacksquare		\blacksquare	
Accomplished less than you would					
like		2	3	4	5
Were limited in the kind of work or					
other activities	1	2	[]3	🔲 4	5
During the past 4 weeks, how much	of the t	ime hav	ve you l	had any	of the
following problems with your work			-	_	
result of any emotional problems (su		_		activiti	ico ao a
result of any emotional problems (si				_ 3	
(se	ICH as I	eening o	lepress	ed or an	
tesure of any emotional problems (se					xious)'
tesure of any emotional problems (se	All of	Most	Some	A little	None
result of any emotional problems (se	All of the	Most of the	Some of the	A little of the	None of the
result of any emotional problems (se	All of	Most	Some	A little	None
result of any emotional problems (se	All of the	Most of the	Some of the	A little of the	None of the
result of any emotional problems (se	All of the	Most of the	Some of the	A little of the	None of the
result of any emotional problems (see	All of the	Most of the	Some of the	A little of the	None of the
	All of the time	Most of the time	Some of the time	A little of the	None of the
Accomplished less than you would like	All of the time	Most of the time	Some of the time	A little of the	None of the
Accomplished less than you would like	All of the time	Most of the time	Some of the time	A little of the	None of the
	All of the time	Most of the time	Some of the time	A little of the time	None of the

5. During the past 4 weeks, how much did pain interfere with your normal work (including both work outside the home and housework)?

Not at all	A little bit	Moderately	Quite a bit	Extremely
lacktriangle	lacktriangle	lacktriangle	lacktriangle	lacktriangle
1	2	3	4	s

CUC10-LNG06-04 Page 37 of 38

6. These questions are about how you feel and how things have been with you during the past 4 weeks. For each question, please give the one answer that comes closest to the way you have been feeling. How much of the time during the past 4 weeks...

	All of the time	Most of the time	Some of the time	A little of the time	None of the time
'	\blacksquare	lacktriangle		▼	
Have you felt calm and peaceful?	🔲 1		🗀	🔲 4	5
ь Did you have a lot of energy?	🗀	2	🗀 з	🗀 4	5
ه Have you felt downhearted and depressed?	 		🗀	🗀	5

7. During the past 4 weeks, how much of the time has your physical health or emotional problems interfered with your social activities (like visiting friends, relatives, etc.)?

All of the time	Most of the time	Some of the time	A little of the time	None of the time
\blacksquare		lacktriangle	lacktriangle	lacktriangle
	2	3	4	5

Thank you for completing these questions!

CUC10-LNG06-04 Page 38 of 38

# **Protocol Summary**

#### Objective

The objective of this study is to assess the feasibility of cryoablation in local tumor control for tumors ≤3.5 cm in patients with pulmonary metastatic disease.

#### Study Design

This is a prospective single-arm feasibility study designed to determine the safety of Galil Medical's Cryoablation System and needles in cryoablation of lung tumors, as well as give an insight into the efficacy of the treatment. All comparisons will be qualitative in nature. Descriptive results of this feasibility study may be used to generate hypotheses for a pivotal study.

This study is to enroll at least 30, but up to 40, patients who will undergo cryoablation of at least 1 metastatic pulmonary tumor via a Galil Medical cryoablation system using Galil Medical cryoablation needles.

Patients will be screened within 6 weeks of the cryoablation procedure. After the cryoablation procedure visit date, follow-up visits will consist of within 1 Week of the cryoablation procedure and then 1, 3, 6, 12, 24, 36, 48 and 60 months post cryoablation procedure.

# Sample Size Justification

Because estimates from this study will be used to power the pivotal study, this study must be able to provide such estimates. A sample size of at least 30 patients, but up to 40 patients, is considered clinically sufficient to give indications of both safety and potential efficacy. This data will be used to decide whether to proceed to a pivotal study, determine endpoints for such a study, and design the study to answer the proposed hypotheses. Up to approximately 10 additional patients may be enrolled to account for patients who do not meet inclusion/exclusion criteria. This study is not powered for formal statistical analysis.

# **General Analysis Methods**

Data will be analyzed using descriptive statistics. Continuous variables (e.g., age) will be summarized by the number of patients, mean, standard deviation, median, interquartile range, minimum and maximum. Categorical variables (e.g., race) will be summarized by frequencies and percentages of patients in each category.

# **Analysis Populations**

All analyses will be performed on the Intent-to-Treat (ITT) population consisting of all subjects treated with a Galil Medical Cryoablation System and needles as the attempted treatment. A per-protocol (PP) analysis may also be done, removing subjects who did not have a complete treatment and those that did not meet the study criteria but were enrolled.

Confidential Page 2 of 9

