11.4. Analysis Populations

All analyses will be performed on all subjects with a Galil Medical Cryoablation System and needles as the attempted treatment. A per-protocol analysis may also be done, removing subjects who did not have a complete treatment and those that did not meet the study criteria but were enrolled.

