#### **Analysis Methods**

Point estimates and two-sided Exact 95% confidence intervals will be generated for events related to the cryoablation procedure in the following categories:

- intra-operative events
- post-operative adverse events
- · serious adverse events
- unanticipated adverse device effects

The safety analysis will be performed on the ITT population. No formal statistical hypothesis testing will be performed for safety endpoints.

Confidential Page 4 of 9

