# Supportive Endpoint Analyses

#### Technically successful treatment

A technically successful treatment will be defined by an ablation volume encompassing the tumor with at least a 5 mm margin. Technical success will be calculated on a per tumor level as well as a patient level. To be considered a technical success on a patient level all tumors treated during the baseline procedure must meet the technical success criteria.

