# **Revision History**

Version	Approval Date	Key Changes
1.0	Sept. 27, 2011	Initial Release
2.0	Aug. 27, 2012	Revised Pooling section to reflect treatment variation between sites/subjects. Added the word "treated" to the Analysis Populations section. Changed "Alquest" to "NAMSA" on signature page to reflect company name change.

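### The SAP adds an undefined 'treated' to the main analysis set, so attempts stopped before freezing may drop out of the safety rates; separately, technical success does not count them as failures

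*SAP*

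**What the plan says.** Protocol 11.4: "All analyses will be performed on all subjects with a Galil Medical Cryoablation System and needles as the attempted treatment". It gives the set no name.

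SAP, Analysis Populations: "All analyses will be performed on the Intent-to-Treat (ITT) population", which consists of "all subjects treated with a Galil Medical Cryoablation System and needles as the attempted treatment". The SAP's Revision History lists the difference as a key change of version 2.0: "Added the word 'treated' to the Analysis Populations section". It gives no reason, and neither document says whether treatment begins at needle insertion, at the first freeze, or at a completed cycle.

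The same SAP section allows an optional per-protocol analysis, "removing subjects who did not have a complete treatment and those that did not meet the study criteria but were enrolled".

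SAP, Safety Endpoint Analysis: "The safety analysis will be performed on the ITT population". Intra-operative events are one of its four reporting categories. For these, "Point estimates and two-sided Exact 95% confidence intervals will be generated". No separate safety population is defined.

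SAP, Technically successful treatment: at patient level, "all tumors treated during the baseline procedure must meet the technical success criteria". Protocol 11.5.4 has the same rule. Neither document states the denominator at tumour level.

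**The concern.** In a feasibility study, an attempt that has to be abandoned is a result. It bears on whether the procedure can be done, and the event that ended it bears on safety. Protocol 8.2.1 leaves the final choice of access route and needle placement to the day of the procedure, and Protocol 6.5 lists pneumothorax and bleeding among the expected risks. An attempt that ends at needle placement is therefore foreseeable.

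Such a patient clearly belongs to the protocol's set. Membership of the SAP's set depends on a word nobody has defined, so the decision could be made after the events are known. The Intent-to-Treat label would lead readers to assume these patients are counted. Both documents say that estimates from this study will be used to power a pivotal study, so a favourable choice of denominator would carry forward.

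**Working it through.** The plan states no figure to reproduce: 30 to 40 patients is a clinical judgement, and there is no power calculation. The check is a comparison of texts, followed by an illustration of size.

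**Step 1. Who is in each set.**

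| Patient | Protocol 11.4 | SAP, Analysis Populations |
|---|---|---|
| Enrolled, procedure never started | Out | Out |
| Needle placed, attempt ended before any freezing | In | Unclear; out if *treated* means freezing was delivered |
| Freezing begun, not completed | In | Apparently in, since incomplete treatment is removed only for the per-protocol analysis |
| Completed | In | In |

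Only the second row is in dispute.

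**Step 2. Technical success for a second-row patient.** Both documents ask whether all treated tumours met the criterion. This patient has none. Suppose 2 of 40 attempts are aborted and the other 38 patients all succeed:

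- Left out of the set, or kept in but unclassified: 38/38 = 100%.
- Kept in, with the rule read literally (no treated tumour failed): 40/40 = 100%.
- Kept in, and counted as failures under a changed rule: 38/40 = 95.0%.

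The move from 100% to 95.0% therefore needs the technical success rule to change. Restoring the protocol's set alone does not produce it.

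**Step 3. Size for technical success, with both changes made.** Inputs: N attempts (30 or 40, from the sample size sections) and a aborts before freezing (assumed, 0 to 4). Every treated patient is assumed to succeed. The treated-only rate is (N − a)/(N − a) = 100%; the attempted rate is (N − a)/N. Intervals are exact (Clopper-Pearson) 95%, the method the SAP names for safety.

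| N | a | Treated only | Attempted, aborts as failures |
|---|---|---|---|
| 40 | 0 | 40/40 = 100% (91.2–100) | 40/40 = 100% (91.2–100) |
| 40 | 1 | 39/39 = 100% (91.0–100) | 39/40 = 97.5% (86.8–99.9) |
| 40 | 2 | 38/38 = 100% (90.7–100) | 38/40 = 95.0% (83.1–99.4) |
| 40 | 4 | 36/36 = 100% (90.3–100) | 36/40 = 90.0% (76.3–97.2) |
| 30 | 1 | 29/29 = 100% (88.1–100) | 29/30 = 96.7% (82.8–99.9) |
| 30 | 4 | 26/26 = 100% (86.8–100) | 26/30 = 86.7% (69.3–96.2) |

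Each abort is worth 1/40 = 2.5 points or 1/30 = 3.3 points.

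**Step 4. Size for safety.** Here the set definition is enough to change the result. With t treated patients and b aborted patients having a related serious adverse event, the rates are t/(N − a) and (t + b)/N. Assume t = 2 and a = 2.

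- Both aborted patients have an event (b = 2), N = 40: 2/38 = 5.3% (0.6–17.7) against 4/40 = 10.0% (2.8–23.7).
- The same with N = 30: 2/28 = 7.1% (0.9–23.5) against 4/30 = 13.3% (3.8–30.7).
- Neither has an event (b = 0), N = 40: 2/38 = 5.3% against 2/40 = 5.0%, a negligible difference.

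**The case against.** The insertion may be no more than an editorial repair. The protocol's sentence lacks a participle, the SAP keeps the reference to attempted treatment beside the new word, and a patient with needles placed could be called treated with the system and needles. The revision entry shows that the edit was deliberate, but not that narrowing was the aim. This stands: the SAP sentence is ambiguous, and exclusion is one reading of it.

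A reader might infer that the SAP swapped *attempted* for *treated* and so discards every aborted or incomplete procedure. The documents do not support that. The per-protocol clause would have nothing to remove if incomplete treatments were already out.

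A reader might also infer that the added word inflates technical success by itself. It does not: Step 2 shows that the existing rule never scores an aborted attempt as a failure, whichever set is used.

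Nor is local control materially affected, because Protocol 11.5.2 and the SAP's efficacy methods already use patients who completed the visit in question as the denominator. Most complications of needle placement will also occur in patients who go on to freezing, and these stay in under any reading.

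Finally, the SAP reports enrolled and evaluable counts and summarises whether cryoablation was completed. A gap would therefore be visible, but it would not enter the rates. The study is descriptive, with no hypothesis test, and the intervals above overlap widely. That limits the harm but does not settle the definition.

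**Conclusion.** The concern holds in a limited form. Two current texts define the main analysis set differently, and the added word is undefined. On one natural reading it removes attempts that ended before freezing from all analyses. The consequence that follows from the wording itself is in safety, where no other set would capture those patients' events. The technical success gap is a separate matter, common to both documents, and lies in the restriction to treated tumours.

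The size is unknown because no abort frequency is given, and it is zero if no attempt ends before freezing. The figures of 5.3% against 10.0% for serious events, and of 100% against 97.5% to 90.0% for technical success at N = 40, rest on assumed counts. The safety contrast also assumes that every aborted patient had a related event. The technical success contrast assumes that all treated patients succeed and that the rule is changed to count aborts as failures. In a study of 30 to 40 patients, one or two such cases would be visible in the reported rates.

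**What to change.** - Delete *treated* from the SAP's Analysis Populations section and put one definition in both documents: all consented subjects in whom the study procedure was started, meaning that a first needle insertion was attempted.
- Use that set for safety and for technical success.
- In Protocol 11.5.4 and the SAP's technical success section, base the patient-level rule on all tumours in which treatment was attempted, so that an aborted attempt counts as a technical failure. State the tumour-level denominator in the same terms.
- Replace the Intent-to-Treat label with *attempted-treatment set*. Keep complete treatment as a condition of the per-protocol analysis only.

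The cost is a few short wording changes in each document, so a protocol amendment is needed as well as an SAP revision. Reported technical success may be slightly lower.

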# **Efficacy Endpoint Analysis**

#### **Efficacy Endpoint**

The efficacy endpoint for this study is local tumor control in patients with pulmonary metastatic disease at 3, 6, 12, 24, 36, 48 and 60 months post cryoablation.

#### **Analysis Methods**

Patients may have up to five tumors so tumor control will be calculated on a per tumor level as well as a patient level. To be considered a success on a patient level all tumors treated during the baseline procedure must meet the tumor control criteria at that follow-up visit.

Post-treatment imaging including CT/MRI will be reported for baseline and follow-up visits. Tumor control for each time point will be determined by examining the change from baseline, and will be defined as:

Complete Response – Tumor disappearance or a  $\geq$  75% decrease in the greatest transaxial diameter ( <25% of original size).

Partial Response – A <75% but ≥30% decrease in the greatest trans-axial diameter.

**Stable Disease** – No change, allowing for a <30% decrease up to a <20% increase in the greatest trans-axial diameter.

**Local Failure** – A ≥20% increase in the greatest trans-axial diameter.

**Local Control** – Local control will be defined as the absence of local failure. Tumors in complete response, partial response and stable disease will all be in local control.

**Distant Failure** – Distant failure (e.g. metastatic disease) will be defined as the appearance of distant cancer deposits consistent with metastatic spread of cancer outside the intended treatment area.

The local tumor control counts and rates will be presented along with the 95% two-sided confidence intervals for the rates. The rate at the each visit will be defined as the proportion of tumors/patients experiencing tumor control at a specific time point out of the number of patients who complete a follow-up visit at that time point.

Efficacy analyses will be performed on the ITT population. Analysis of the PP population may be done in support of the ITT analysis. No formal statistical hypothesis testing will be performed for efficacy endpoints.

Confidential Page 3 of 9

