9.7.3. Partial Response

Partial response will be defined as >30% decrease in the sum of the largest diameter of all targeted tumors.

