9.7.4. Stable Disease

Stable disease will be defined as <30% decrease in the sum of the largest diameter of all targeted tumors.

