9.7.5. Local Failure

Local failure will be defined as >20% increase in the sum of the largest diameter of all targeted tumors.

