11.5.2. Efficacy Endpoints

The efficacy endpoint for this study is defined as follows: local tumor control in patients with pulmonary metastatic disease at 3, 6, 12, 24, 36, 48 and 60 months post cryoablation.

Tumor control will be determined by examining the change from baseline at follow-up visits. Post-treatment imaging including CT/MRI will be reported for baseline and follow-up visits. Tumor control will be defined by the criteria defined in Section 9.7 of this protocol.

CUC10-LNG06-04 Page 19 of 38

Patients are allowed up to 5 tumors so tumor control will be calculated on a per tumor level as well as a patient level. To be considered a success on a patient level all tumors treated during the baseline procedure must meet the tumor control criteria at that follow-up visit.

The local tumor control counts and rates will be presented along with the 95% two-sided confidence intervals for the rates. The rate at the each visit will be defined as the proportion of tumors/patients experiencing tumor control at a specific timepoint out of the number of patients who complete a follow-up visit at that timepoint.

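### Local failure is judged on summed diameters in Protocol 9.7.3-9.7.5 but tumor by tumor in the SAP, so a patient with two or more treated tumors can be controlled under one and failed under the other

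*SAP*

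**What the plan says.** Protocol 9.7 takes baseline size from the pretreatment CT or MRI, and 9.7.1 treats local control as the absence of local failure. The categories that follow are set on a total over tumors: "Partial response will be defined as >30% decrease in the sum of the largest diameter of all targeted tumors" (9.7.3), "Stable disease will be defined as <30% decrease in the sum of the largest diameter of all targeted tumors" (9.7.4) and "Local failure will be defined as >20% increase in the sum of the largest diameter of all targeted tumors" (9.7.5).

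Protocol 11.5.2 refers the analysis to those categories: "Tumor control will be defined by the criteria defined in Section 9.7 of this protocol". The same section asks for control per tumor and per patient, and for patient-level success it says that "all tumors treated during the baseline procedure must meet the tumor control criteria at that follow-up visit". It fixes the reference as well: "Tumor control will be determined by examining the change from baseline at follow-up visits".

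The SAP (Efficacy Endpoint Analysis, Analysis Methods) repeats the per-tumor and all-tumors requirement but gives its own categories, introduced by "Tumor control for each time point will be determined by examining the change from baseline, and will be defined as". There, local failure is a "≥20% increase in the greatest trans-axial diameter". The failure line does not itself say that it applies to each tumor. That reading follows from the per-tumor calculation in the same section, from its statement that tumors in complete response, partial response or stable disease are in control, and from the per-tumor response listed under Imaging and lung function.

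Recurrence or progression is a separate time-to-event endpoint in both documents (Protocol 11.5.4; SAP, Disease recurrence or progression). It is triggered by growth and/or contrast enhancement.

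**The concern.** The definitions differ in three ways: the unit (sum or single tumor), the threshold (above 20%, or 20% and above) and the diameter named (largest, or greatest trans-axial). The protocol is also at odds with itself, because 11.5.2 needs a verdict on each tumor and a sum over tumors does not supply one. In the text available, neither document says which definition prevails.

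The eligibility criteria allow several treated tumors per patient, so the conflict can arise by design. Protocol 11.2 intends the study's estimates to power a pivotal study, and an estimate carried forward needs one definition.

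The secondary point is the reference scan. Both documents judge every visit only against pretreatment size. After ablation, a lesion may shrink and then grow back, and such regrowth can stay within the control categories.

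**Working it through.** The plan gives no figure on this point to reproduce. The check applies both rules to the same diameters. The example diameters are assumptions, with baseline sizes within the 3.5 cm limit of Protocol 7.2.5.

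**Rules.** Let b be a tumor's baseline diameter and d its diameter at a visit.
- Protocol 9.7.5: failure if (sum of d)/(sum of b) - 1 > 0.20.
- SAP: a tumor fails if d/b - 1 >= 0.20; the patient is controlled only if no treated tumor fails.

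**One treated tumor.** Both reduce to d/b - 1. For 30 to 35 mm the change is +16.7%, controlled under both. For 30 to 36 mm it is exactly +20%: controlled under the protocol, failure under the SAP. Otherwise the rules agree, unless the two named diameters differ.

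**Two or more treated tumors.**

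| Baseline (mm) | Visit (mm) | Sum change | Protocol 9.7.5 | Largest single change | SAP, patient level |
|---|---|---|---|---|---|
| 20, 20 | 30, 10 | 40 to 40, 0% | control | +50% | failure |
| 30, 10 | 15, 18 | 40 to 33, -17.5% | control | +80% | failure |
| 30, 30, 10 | 20, 20, 30 | 70 to 70, 0% | control | +200% | failure |

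With k equal tumors of which one grows by a fraction g and the rest are unchanged, the sum changes by g/k. The sum rule calls no failure while g <= 0.20k: up to 40% growth for k = 2 and 60% for k = 3. The SAP calls failure at 20% in each case.

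**Direction.** If every tumor is below 1.20 times its own baseline, the sum is below 1.20 times the baseline sum. So whenever the sum rule calls failure, at least one tumor fails under the SAP rule. For the same diameters, the protocol's patient-level control rate is therefore equal to or higher than the SAP's, never lower.

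**Regrowth.** Take 30 mm, then 6 mm, then 35 mm. The middle scan is 6/30 - 1 = -80%, a complete response in the SAP. The last is 35/30 - 1 = +16.7% from baseline, so controlled under both rules, although 35/6 - 1 = +483% from the smallest size. In general, a tumor whose smallest size was a fraction f of baseline reaches the SAP failure threshold only at 1.20/f times that size: 4.8-fold for f = 0.25 and 1.71-fold for f = 0.70.

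**Effect of one patient.** 1/40 = 2.5 percentage points; 1/30 = 3.3 points. These take the planned 30 to 40 patients as all evaluable at the visit; with fewer attending, each patient counts for more.

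**The case against.** The strongest defense is that the analysis sections already settle the matter. Protocol 11.5.2 asks for control per tumor and requires every treated tumor to be controlled. Applied to a single tumor, a sum is just that tumor's diameter, which is nearly the SAP rule. On that view the sum wording is a leftover. The reading is sensible and probably what was meant, but no passage states it. An analyst who follows the reference to Section 9.7 as written gets the other rule.

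On regrowth the defense is stronger. A reader might infer that the baseline reference is an error, or that regrowth goes unrecorded. The documents support neither. Both choose change from baseline consistently, and nothing in them promises a smallest-size reference. Progression is assessed at the imaging visits from Month 3 (Protocol 8.5, 8.6), the recurrence endpoint can register growth or enhancement, and diameters are summarized per tumor. What remains is narrower: recurrence does not feed local control, so one visit can show both recurrence and control.

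The stakes are also limited. The study is descriptive and tests no hypothesis. At an assumed 36 of 40 controlled, the exact 95% interval is 76.3% to 97.2%, wide beside a shift of 2.5 points. That limits the urgency, but it does not justify two definitions of the only efficacy endpoint.

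**Conclusion.** The conflict in definitions is wrong as written and should be reconciled before analysis. It affects patients with two or more treated tumors, for whom the two rules can give opposite results. With one tumor they differ only at exactly 20% or where the two diameters differ. The direction is certain for the same diameters: the sum rule can only miss failures that the SAP rule calls.

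The regrowth point is factually right, but it supports an added analysis, not a correction.

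A reader might go further and conclude that the reported control rate will be inflated by a material amount. The documents do not support that. They give neither the number of patients with several treated tumors nor the share of regrowths that stay below 120% of baseline, and if the SAP is followed the stricter rule applies. Only the unit effect can be stated: 2.5 points per reclassified patient with 40 evaluable, 3.3 with 30.

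**What to change.** **Required.** Replace the sum wording in Protocol 9.7.3-9.7.5 with the SAP's per-tumor definitions. Use one threshold and one diameter (greatest trans-axial) in both documents, and state that patient-level control requires every treated tumor to be controlled. This costs wording only.

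**Cheap improvement.** Keep the baseline-referenced rate and add a supportive local control rate. In it, a tumor fails on a 20% or greater increase over its smallest diameter among baseline and the scheduled CT/MRI scans from Month 3 up to, but not including, the current visit. Month 3 is then judged against baseline, and a later scan cannot turn an earlier visit into a failure. Week 1 imaging is left out because it may be an X-ray. Count reappearance after a recorded 0 mm as failure, cite the recording convention of Protocol 9.7.2 in the SAP, and state a minimum absolute increase in advance.

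**Cost.** No new scans are needed: CT/MRI is already scheduled from Month 3, and the SAP already lists greatest trans-axial diameter per tumor. The supportive rate may be lower than the baseline-referenced one. It is also sensitive to measurement error in small lesions, since 20% of the 5 mm default is 1 mm. The documents give no minimum absolute increase, so the sponsor must choose and justify one.

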8.2.1. Cryoablation needle placement

Based upon isotherm data for the cryoablation needles, the distance between adjacent cryoablation needles should be ≤ 15 mm. The number and configuration of the needles will be

CUC10-LNG06-04 Page 14 of 38

based on the necessity to maintain appropriate distances between adjacent cryoablation needles and anatomic structures, and the final number of needles can only be formulated based upon the configuration of the lung tumor at the time of treatment.

The CT imaging views of the lung tumor will enable final assessment of the percutaneous access route and needle placement on the day of the procedure. Cryoablation needles will be placed to create multiple overlapping iceballs to completely cover the tumor and provide a 5 mm zone of ablation surrounding the tumor while maintaining appropriate safe distance from the non-targeted tissues (i.e. main bronchus and pulmonary arteries).

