9.7. Response Determination

The tumor(s) treated will be defined as the target tumor. The baseline size(s) will be measured on the pretreatment CT/MRI scan.

Local tumor control will be defined as follows:

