9.7.1. Local Control

Local control will be defined as the absence of local failure.

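### A new tumor nodule inside the intended treatment area fits no failure category, so it counts by default as local control

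*SAP*

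**What the plan says.** Local tumor control at 3 to 60 months is the only efficacy endpoint. It rests on four linked definitions.

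- **Local failure.** SAP, Analysis Methods (efficacy): "A ≥20% increase in the greatest trans-axial diameter", judged as change from baseline. Protocol 9.7.5: "Local failure will be defined as >20% increase in the sum of the largest diameter of all targeted tumors". Both are growth thresholds on treated tumors, and neither mentions new lesions. Protocol 9.7 fixes what is measured: "The tumor(s) treated will be defined as the target tumor".
- **Distant failure.** In both documents, "distant cancer deposits consistent with metastatic spread of cancer outside the intended treatment area".
- **Local control.** Protocol 9.7.1: "Local control will be defined as the absence of local failure". The SAP repeats this and adds that complete response, partial response and stable disease all count as control.
- **Patient-level success.** "all tumors treated during the baseline procedure must meet the tumor control criteria at that follow-up visit". Only tumors treated at baseline are considered.

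The treated area is larger than the tumor. Protocol 8.2.1 has needles placed to cover the tumor and "provide a 5 mm zone of ablation surrounding the tumor". Protocol 8.2.3 and the SAP's definition of technical success make 5 mm a minimum. Neither document defines the intended treatment area.

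A separate endpoint, time to recurrence or progression (Protocol 11.5.4; SAP, Disease recurrence or progression), counts tumor growth, contrast enhancement, or both, and is analyzed by Kaplan-Meier. The SAP also lists the number of new tumors at follow-up as a descriptive summary (Imaging and lung function).

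**The concern.** Regrowth within or at the edge of the ablated zone is what a local control endpoint should detect. Here the two failure categories leave a gap. Local failure looks only at the size of the treated tumor, and distant failure looks only outside the treated area. A new deposit inside the area but separate from the measured tumor is assigned to neither. Because control is the residual category, anything unassigned is scored as success.

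There is no hypothesis test, so no error rate is at stake. What is at stake is a descriptive estimate. Protocol 11.2 and the SAP's Sample Size Justification say that estimates from this study will inform whether to proceed to a pivotal study and how to power it.

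**Working it through.** The plan states no expected control rate, so there is no figure to reproduce. The check is first of definitions, then of scale.

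**1. Classify a new nodule inside the treated area, separate from a treated tumor that has not grown.**

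| Rule | Met? | Reason |
|---|---|---|
| Local failure, SAP | No | The treated tumor's diameter has not risen by 20% |
| Local failure, Protocol 9.7.5 | No | The nodule is not a treated tumor, so it is not in the sum |
| Distant failure | No | The nodule is not outside the area |
| Local control | Yes | Local failure is absent |
| Recurrence or progression | Possibly | Enhancement alone can qualify |

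One scan can therefore be a local control success and a recurrence event. Nothing links the two endpoints, and the new-tumor count does not enter the control rate.

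**2. Would measuring the nodule as part of the treated tumor close the gap?** Not reliably. Under the SAP, failure starts at 1.2 × baseline diameter.

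- Baseline 2.0 cm: 1.2 × 2.0 = 2.4 cm. If the tumor vanishes and a 1.5 cm nodule is recorded in its place, the change is (1.5 − 2.0)/2.0 = −25%, which is stable disease. A 0.8 cm nodule gives −60%, a partial response.
- Baseline 3.5 cm, the eligibility maximum: 1.2 × 3.5 = 4.2 cm.

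**3. Effect per event.** The denominator is patients completing the visit. One misclassified patient moves the patient-level rate by 1/n.

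- n = 30: 1/30 = 3.3 points.
- n = 40: 1/40 = 2.5 points.
- The effect is larger at later visits if fewer patients attend.

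Illustration, assuming 90% apparent control. Intervals are exact 95%; the SAP does not name the method for the efficacy rate.

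| Patients reclassified | n = 30 | n = 40 |
|---|---|---|
| 0 | 90.0% (73.5 to 97.9) | 90.0% (76.3 to 97.2) |
| 1 | 86.7% (69.3 to 96.2) | 87.5% (73.2 to 95.8) |
| 2 | 83.3% (65.3 to 94.4) | 85.0% (70.2 to 94.3) |
| 3 | 80.0% (61.4 to 92.3) | 82.5% (67.2 to 92.7) |

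**4. Outer bound.** The 20-patient, 35-tumor series in Protocol 3.2 reports local recurrence in 7/35 = 20% of tumors and 7/20 = 35% of patients. Let s be the share of recurrences that appear as new nodules in the treated area and are missed by the growth rule. The overstatement is 20 × s points per tumor and 35 × s per patient. The documents do not give s. With s from 0 to 1, the range is 0 to 20 points per tumor and 0 to 35 per patient.

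**The case against.** The strongest case on the other side has four parts.

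- **The geometry is narrow.** A roughly round nodule lying wholly within a 5 mm rim and not touching the tumor is under 5 mm across. As it grows, it meets the tumor and may be included in its diameter, or it extends outside the area and may be called distant. This limits how often the gap applies but does not close it. Margins may exceed 5 mm, merging need not reach 20% growth (step 2), and no rule says how an adjoining nodule is measured.
- **Recurrence is captured elsewhere.** Progression is assessed at every visit from Month 3 and analyzed separately, so the event is not lost to the study. That stands. It still does not correct the control rate.
- **Measurement could err the other way.** A 5 mm margin adds 1.0 cm to the diameter: 1.0/3.5 = +28.6% at the largest eligible size, and more for smaller tumors. If a reader measured the ablation zone instead of the tumor, a successful ablation would be scored as local failure. The documents do not say that readers do this. It is a separate ambiguity and does not cancel this one, but it means the net direction of all measurement effects is not established.
- **The study is descriptive.** True. It limits the consequence to the estimate and its later use.

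A reader might infer that the reported rate is overstated as a matter of fact. The documents do not support that: such nodules must occur, and must not be captured as growth of the target. A reader might also pick a share, say a quarter to three quarters of recurrences, and quote 5 to 15 points per tumor and 9 to 26 per patient. No source in the documents supports any share or excludes zero. Nor does the protocol say how the cited series defined local recurrence, and that series used another manufacturer's probes on tumors under 3 cm.

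**Conclusion.** The gap is real in both documents and lies in the only efficacy endpoint. On the literal wording, a new nodule inside the intended treatment area counts as local control for tumor and patient, and may be a recurrence on the same scan. Taken alone, the rule can only raise the control rate. It does so only if such nodules occur and the growth rule misses them.

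The supportable size is 3.3 points per misclassified patient at n = 30 and 2.5 at n = 40. The 0 to 20 and 0 to 35 point ranges are outer bounds from one cited series, not forecasts for this trial. No error rate or sample size calculation is affected. The change should be made because the estimate is meant to inform a pivotal study. Without a rule, sites may also classify the same finding differently, although the SAP's poolability argument assumes common outcome assessment.

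**What to change.** 1. Define the intended treatment area in both documents as the target tumor plus the planned ablation margin (at least 5 mm, as the protocol already states).
2. Add to Local Failure in the SAP's Analysis Methods and in Protocol 9.7.5: *or any new tumor nodule within or touching the intended treatment area, regardless of the size category of the treated tumor*. The last clause sets precedence, so that a small nodule where a tumor had vanished is not scored as partial response.
3. Require every new deposit to be classed as either local or distant failure.
4. Reconcile local failure with the recurrence endpoint, including how enhancement without growth is treated.
5. Reconcile the two growth rules: at least 20% per tumor in the SAP, more than 20% of the summed diameters in the protocol. Both documents ask for a tumor-level rate, which a sum over all tumors cannot supply.

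The cost is a short text change and one added eCRF item. The planned scans suffice. The control rate may come out less favourable.
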